## **6.5 Pharmacodynamics**

### **6.5.1 Collection of pharmacodynamic markers**

Pharmacodynamic measurements will include IPA (final extent, 20µm ADP) and the VerifyNow™ P2Y12 assay. Blood samples for pharmacodynamics measurements will be collected at the time points outlined in Table 2. The PD sample should always precede the PK sample, should difficulty occur obtaining PK or PD blood samples, the PD blood sample takes priority.

The actual times of every sample drawn may change but the number of samples will remain the same. All efforts will be made to obtain the pharmacodynamics and pharmacokinetic samples at the exact nominal time relative to dosing. However, samples obtained within 10% of the nominal time (eg, within 6 minutes of a 60 minute sample) from dosing will not be captured as a protocol deviation, as long as the exact time of the sample collection is noted on the source document and data collection tool (eg, eCRF).

Samples will be collected, labelled, stored and shipped as detailed in the Laboratory Manual.

For blood volume see Section 7.1.

### **6.5.2 IPA by LTA**

#### **6.5.2.1 Methods of assessment**

4.5 mL Blood samples for pharmacodynamics measurements will be drawn through the same cannula used for the PK sampling and will be collected at the time points outlined in Table 2.

The samples will be maintained at room temperature until centrifugation. The study specific laboratory manual contains a detailed description of the process and procedure.

### **6.5.3 VerifyNow™ P2Y12 assay**

#### **6.5.3.1 Methods of assessment**

A 2 mL blood sample will be collected for P2Y12 assay. The VerifyNow™ System (Accumetrics, San Diego, CA) is a turbidimetric based optical detection system that measures platelet aggregation in whole blood (Aleil B et al 2005, Barragan P et al 2003). The assay device contains a lyophilised preparation of human fibrinogen-coated beads, platelet activators, and buffer. The assay is based upon the ability of activated platelets to bind fibrinogen. Fibrinogen-coated micro-particles aggregate in whole blood in proportion to the number of expressed platelet GPIIb/IIIa receptors. The rate of micro-bead aggregation is more rapid and reproducible if platelets are activated; therefore, the reagent adenosine-5-diphosphate (ADP/PGE1) is incorporated into the assay channel to induce platelet activation without fibrin formation.

For blood volume see Section 7.1.

## 7. BIOLOGICAL SAMPLING PROCEDURES

### 7.1 Volume of blood

The total volume of blood that will be drawn from each patient in this study is as follows:

**Table 6 Volume of Blood**

Volume of Blood to be Drawn from Each Patient				
Assessment		Sample Volume a (mL)	No. of Samples	Total Volume (mL)
Safety	Clinical chemistry	4	3	12
	Haematology	2	3	6
Serology b		4	1	4
Pharmacokinetic		2	17	34
VerifyNow™ P2Y 12		2	17	34
Discard sample prior to PD/PK sample c		1	17	17
Platelet Aggregation (LTA)		4.5	17	76.5
FSH		4	1	4
Coagulation test		2	1	2
Total (approximately)				189.5

aThe sample volume for safety assessments, Serology, serum  $\beta$ -HCG are approximate volumes that are patient to site-specific change.

bThe Serology test includes: Hepatitis B surface antigen; Anti HCV IgG; HIV. The blood taken for Serology will be combined with chemistry at screening.

cThis discarded blood from predraws used to remove fluid from flushed catheters, the discarded volume is not expected to exceed 1 mL for each PK or PD draw point.

### 7.2 Handling, storage and destruction of biological samples

The samples will be used up or disposed of after analyses and the clinical study report has been finalized.

#### 7.2.1 Pharmacokinetic samples

Pharmacokinetic samples will be disposed of or anonymised by pooling after the Bioanalytical Report finalization or six months after issuance of the draft Bioanalytical Report (whichever is earlier), unless requested for future analyses. Pooled, anonymised samples may be used for analytical method and/or validation.

Incurring sample reproducibility analysis, if any, will be performed alongside the bioanalysis of the test samples. The results from the evaluation will not be reported in the Clinical Study Report but separately in a Bioanalytical Report.

### **7.2.2 Pharmacodynamic samples**

Samples will be disposed of after the clinical study report has been finalised.

### **7.3 Labelling and shipment of biohazard samples**

The Principal Investigator ensures that samples are labelled and shipped in accordance with the Laboratory Manual and the Biological Substance, Category B Regulations (materials containing or suspected to contain infectious substances that do not meet Category A criteria), see Appendix C 'IATA 6.2 Guidance Document'.

Any samples identified as Infectious Category A materials are not shipped and no further samples will be taken from the patient unless agreed with AstraZeneca and appropriate labelling, shipment and containment provisions are approved.

### **7.4 Chain of custody of biological samples**

A full chain of custody is maintained for all samples throughout their lifecycle.

The Principal Investigator keeps full traceability of collected biological samples from the patients while in storage at the centre until shipment or disposal (where appropriate) and keeps documentation of receipt of arrival.

The sample receiver keeps full traceability of the samples while in storage and during use until used or disposed of or until further shipment and keeps documentation of receipt of arrival.

AstraZeneca keeps oversight of the entire life cycle through internal procedures, monitoring of study sites and auditing of external laboratory providers.

Samples retained for further use are registered in the AstraZeneca biobank system during the entire life cycle.

### **7.5 Withdrawal of informed consent for donated biological samples**

If a patient withdraws consent to the use of donated biological samples, the samples will be disposed of/destroyed, and the action documented. If samples are already analysed, AstraZeneca is not obliged to destroy the results of this research.

As collection of the biological samples is an integral part of the study, then the patient is withdrawn from further study participation.

The Principal Investigator:

- Ensures patients' withdrawal of informed consent to the use of donated samples is notified immediately to AstraZeneca
- Ensures that biological samples from that patient, if stored at the study site, are immediately identified, disposed of /destroyed, and the action documented

- Ensures the laboratory(ies) holding the samples is/are informed about the withdrawn consent immediately and that samples are disposed/destroyed, the action documented and the signed document returned to the study site
- Ensures that the patient and AstraZeneca are informed about the sample disposal.

AstraZeneca ensures the central laboratory(ies) holding the samples is/are informed about the withdrawn consent immediately and that samples are disposed of/destroyed and the action documented and returned to the study site.

## **8. ETHICAL AND REGULATORY REQUIREMENTS**

### **8.1 Ethical conduct of the study**

The study will be performed in accordance with ethical principles that have their origin in the Declaration of Helsinki and are consistent with ICH/Good Clinical Practice, applicable regulatory requirements and the AstraZeneca policy on Bioethics and Human Biological Samples.

### **8.2 Patient data protection**

The Informed Consent Form will incorporate (or, in some cases, be accompanied by a separate document incorporating) wording that complies with relevant data protection and privacy legislation.

### **8.3 Ethics and regulatory review**

An Ethics Committee should approve the final study protocol, including the final version of the Informed Consent Form and any other written information and/or materials to be provided to the patients.

The opinion of the Ethics Committee should be given in writing. The investigator should submit the written approval to AstraZeneca before enrolment of any patient into the study.

The Ethics Committee should approve all advertising used to recruit patients for the study.

AstraZeneca should approve any modifications to the Informed Consent Form that are needed to meet local requirements.

If required by local regulations, the protocol should be re-approved by the Ethics Committee annually.

Before enrolment of any patient into the study, the final study protocol, including the final version of the Informed Consent Form, is approved by the national regulatory authority or a notification to the national regulatory authority is done, according to local regulations.

AstraZeneca will handle the distribution of any of these documents to the national regulatory authorities.

AstraZeneca will provide Regulatory Authorities, Ethics Committees and Principal Investigators with safety updates/reports according to local requirements, including SUSARs (Suspected Unexpected Serious Adverse Reactions), where relevant.

#### **8.4 Informed consent**

The Principal Investigator(s) at each centre will:

- Ensure each patient is given full and adequate oral and written information about the nature, purpose, possible risk and benefit of the study
- Ensure each patient is notified that they are free to discontinue from the study at any time
- Ensure that each patient is given the opportunity to ask questions and allowed time to consider the information provided
- Ensure each patient provides signed and dated informed consent before conducting any procedure specifically for the study
- Ensure the original, signed Informed Consent Form(s) is/are stored in the Investigator's Study File
- Ensure a copy of the signed Informed Consent Form is given to the patient
- Ensure that any incentives for patients who participate in the study as well as any provisions for patients harmed as a consequence of study participation are described in the informed consent form that is approved by an Ethics Committee.

#### **8.5 Changes to the protocol and informed consent form**

Study procedures will not be changed without the mutual agreement of the Principal Investigator and AstraZeneca.

If there are any substantial changes to the study protocol, then these changes will be documented in a study protocol amendment and where required in a new version of the study protocol (Revised Clinical Study Protocol).

The amendment is to be approved by the relevant Ethics Committee and if applicable, also the national regulatory authority approval, before implementation. Local requirements are to be followed for revised protocols.

AstraZeneca will distribute any subsequent amendments and new versions of the protocol to each Principal Investigator(s). For distribution to Ethics Committee see Section 8.3.

If a protocol amendment requires a change to a centre's Informed Consent Form, AstraZeneca and the centre's Ethics Committee are to approve the revised Informed Consent Form before the revised form is used.

If local regulations require, any administrative change will be communicated to or approved by each Ethics Committee.

## **8.6 Audits and inspections**

Authorised representatives of AstraZeneca, a regulatory authority, or an Ethics Committee may perform audits or inspections at the centre, including source data verification. The purpose of an audit or inspection is to systematically and independently examine all study-related activities and documents, to determine whether these activities were conducted, and data were recorded, analysed, and accurately reported according to the protocol, Good Clinical Practice (GCP), guidelines of the International Conference on Harmonisation (ICH), and any applicable regulatory requirements. The investigator will contact AstraZeneca immediately if contacted by a regulatory agency about an inspection at the centre.

## **9. STUDY MANAGEMENT BY ASTRAZENECA**

### **9.1 Pre-study activities**

Before the first patient is entered into the study, it is necessary for a representative of AstraZeneca to visit the investigational study site to:

- Determine the adequacy of the facilities
- Determine availability of appropriate patients for the study
- Discuss with the investigator(s) (and other personnel involved with the study) their responsibilities with regard to protocol adherence, and the responsibilities of AstraZeneca or its representatives. This will be documented in a Clinical Study Agreement between AstraZeneca and the investigator.

### **9.2 Training of study site personnel**

Before the first patient is entered into the study, an AstraZeneca representative will review and discuss the requirements of the Clinical Study Protocol and related documents with the investigational staff and also train them in any study specific procedures and *the WBDC* system(s) utilised.

The Principal Investigator will ensure that appropriate training relevant to the study is given to all of these staff, and that any new information relevant to the performance of this study is forwarded to the staff involved.

The Principal Investigator will maintain a record of all individuals involved in the study (medical, nursing and other staff).

### **9.3 Monitoring of the study**

During the study, an AstraZeneca representative will have regular contacts with the study site, including visits to:

- Provide information and support to the investigator(s)
- Confirm that facilities remain acceptable
- Confirm that the investigational team is adhering to the protocol, that data are being accurately and timely recorded in the CRFs, that biological samples are handled in accordance with the Laboratory Manual and that study drug accountability checks are being performed
- Perform source data verification (a comparison of the data in the CRFs with the patient's medical records at the hospital or practice, and other records relevant to the study) including verification of informed consent of participating patients. This will require direct access to all original records for each patient (eg, clinic charts)
- Ensure withdrawal of informed consent to the use of the patient's biological samples is reported and biological samples are identified and disposed of/destroyed accordingly, and the action is documented, and reported to the patient.

The AstraZeneca representative will be available between visits if the investigator(s) or other staff at the centre needs information and advice about the study conduct.

#### **9.3.1 Source data**

Refer to the Clinical Study Agreement for location of source data.

### **9.4 Study agreements**

The Principal Investigator at each/the centre should comply with all the terms, conditions, and obligations of the Clinical Study Agreement, or equivalent, for this study. In the event of any inconsistency between this Clinical Study Protocol and the Clinical Study Agreement, the terms of Clinical Study Protocol shall prevail with respect to the conduct of the study and the treatment of patients and in all other respects, not relating to study conduct or treatment of patients, the terms of the Clinical Study Agreement shall prevail.

Agreements between AstraZeneca and the Principal Investigator should be in place before any study-related procedures can take place, or patients are enrolled.

#### **9.4.1 Archiving of study documents**

The Investigator follows the principles outlined in the Clinical Study Agreement (CSA).

## **9.5 Study timetable and end of study**

The end of the study is defined as ‘the last visit of the last patient undergoing the study’.

The study is expected to start in Q1, 2014 and to end by Q4, 2014.

The study may be terminated at individual centres if the study procedures are not being performed according to GCP, or if recruitment is slow. AstraZeneca may also terminate the entire study prematurely if concerns for safety arise within this study or in any other study with ticagrelor.

## **10. DATA MANAGEMENT BY ASTRAZENECA**

Data management will be performed by Cognizant.

The data collected through third party sources will be obtained and reconciled against study data.

Adverse events and medical/surgical history will be classified according to the terminology of the latest version the Medical Dictionary for Regulatory Activities (MedDRA). Medications will be classified according to the AstraZeneca Drug Dictionary. All coding will be performed by the Medical Coding Team at the Cognizant Data Management Centre.

Data queries will be raised for inconsistent, impossible or missing data. All entries to the study database will be available in an audit trail.

The data will be validated as defined in the Data Management Plan. Quality control procedures will be applied to each stage of data handling to ensure that all data are reliable and have been processed correctly.

When all data have been coded, validated, signed and locked, clean file will be declared. Any treatment revealing data may thereafter be added and the final database will be locked.

Data associated with biological samples will be transferred to laboratories internal or external to AstraZeneca.

## **11. EVALUATION AND CALCULATION OF VARIABLES BY ASTRAZENECA**

### **11.1 Calculation or derivation of safety variable(s)**

Where appropriate, change-from-baseline variables will be calculated for the continuous variables as the post-treatment value minus the value at baseline.

Baseline for Haematology and Clinical Chemistry will be defined as the value measured Day-1. If a patient is missing the baseline collection, the previous non-missing evaluation will become the baseline value. If no baseline or previous-to-baseline evaluation exists then the baseline value will be treated as missing.

### **11.1.1 Other significant adverse events (OAE)**

During the evaluation of the AE data, an AstraZeneca medically qualified expert will review the list of AEs that were not reported as SAEs and DAEs. Based on the expert's judgement, significant adverse events of particular clinical importance may, after consultation with the Global Patient Safety Physician, be considered OAEs and reported as such in the Clinical Study Report. A similar review of laboratory/vital signs data will be performed for identification of OAEs.

Examples of these are marked haematological and other laboratory abnormalities, and certain events that lead to intervention (other than those already classified as serious), dose reduction or significant additional treatment.

## **11.2 Calculation or derivation of pharmacokinetic variables**

Pharmacokinetic analyses will be performed by AstraZeneca R&D.

Plasma concentrations of ticagrelor and its metabolite AR-C124910XX will be listed and depicted graphically as a function of time relative to dose. The following pharmacokinetic parameters will be estimated by non-compartmental analysis:

- Single dose:  $C_{max}$ ,  $t_{max}$ ,  $t_{1/2}$  and  $AUC_{0-t}$ , and AUC of ticagrelor and AR-C124910XX.
- Multiple doses:  $C_{max}$ ,  $t_{max}$  of ticagrelor and AR-C124910XX.

Ticagrelor and AR-C124910XX  $C_{max}$  will be estimated as the highest measured concentration and  $t_{max}$  will be the time to maximum concentration following dosing. The terminal phase elimination constant ( $\lambda_z$ ) will be calculated by log-linear regression of the terminal portion of the concentration-time profile using at least 3 time points. The terminal elimination half-life ( $t_{1/2}$ ) will be calculated as  $0.693/\lambda_z$ . AUC will be calculated using the linear trapezoidal method up to the last measurable concentration ( $AUC_{0-t}$ ) and thereafter by extrapolation of the terminal elimination phase to infinity. The ratio of AR-C124910XX  $C_{max}$  to ticagrelor  $C_{max}$  ratio and, AR-C124910XX AUC to ticagrelor AUC ratio will be calculated. Accumulation ratio (AR) of ticagrelor and AR C124910XX will be estimated as a ratio of Day 7 AUC(0-12h) to Day 1 AUC(0-12h).

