However, both ticlopidine and clopidogrel have a slow onset of action at the platelet ADP receptor, and their pharmacologic inhibition of platelet aggregation has been reported as irreversible and incomplete. Approximately 15% to 30% of patients treated with clopidogrel were reported as non-responders to clopidogrel therapy (Gurbel PA et al 2003, Järemo et al 2002, Muller et al 2003). Nonresponders have a higher rate of ischemic events during clopidogrel treatment (Aleil B et al 2005, Barragan P et al 2003, Matetzky S et al 2004, Price MJ et al 2006). In addition, the slow offset of clopidogrel's effect is problematic in the current strategy of administering clopidogrel therapy before percutaneous coronary intervention (PCI) in patients with undefined, diseased coronary anatomy, as these patients have an increased risk of bleeding if administered clopidogrel within 5-7 days of undergoing coronary artery bypass graft surgery (Hongo RH et al 2002). Therefore, the development of new ADP receptor antagonists with improved efficacy and/or safety profiles is desirable.

Ticagrelor is orally active and does not require metabolic activation. Ticagrelor binds to plasma proteins (>99.7%), is extensively metabolised by cytochrome P450 3A (CYP3A), the elimination half-life ( $t_{1/2}$ ) of the parent compound is approximately 7 hours and the primary metabolite, AR-C124910XX, is considered equipotent to the parent drug *in vitro*. Additional information on ticagrelor is available in the investigator's brochure.

Ticagrelor is approved with low doses of ASA (75-100 mg daily). Therefore, the current study will limit the dose of ASA to 75 to 100mg daily.

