### **3.2 Rationale for study design, doses and control groups**

The primary objective is to determine the IPA profiles of single and multiple doses of ticagrelor 45, 60, and 90 mg in Chinese patients with stable coronary heart disease on chronic low dose ASA. The primary variable is IPA, final extent (20 $\mu$ M ADP). Previous exposure of ticagrelor in China includes healthy patients (D5130C00054) and ACS patients (D5130C05262), but not stable coronary heart disease. This study will explore three doses of ticagrelor in order to determine the IPA, PRU and pharmacokinetic profile in Chinese patients with stable coronary heart disease. The VerifyNow System is a commercially available system to measure inhibition of P2Y12 receptor and is considered appropriate for this study. Holter monitoring and an echocardiogram will be obtained prior to dosing in order to rule out those at risk for bradyarrhythmias and potential indications for anticoagulation. See Section 4.2

This is an open label, single centre, randomised, Phase IV, pharmacodynamic, pharmacokinetic, and safety study. There is no control group.

Treatment for 4 days with bid dosing of the study allows ticagrelor to reach steady-state, and hence allows Day 7 results to be compared with the Day 1 dose of each drug dose level.

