## **6.4 Pharmacokinetics**

### **6.4.1 Collection of samples**

Blood samples (2 mL) for determination of ticagrelor and its metabolite AR-C214910XX in plasma will be taken at the times presented in the study plan Table 2.

On Days 1, 2, 3, blood samples for pharmacokinetic analysis of ticagrelor and its metabolite AR-C214910XX will be obtained of each treatment group at the following time points:

- Pre-dose (within 120 minutes prior to dosing), 0.5, 1, 2, 3, 6, 12, 24, 36, and 48 hours post dose.

On Day 7, blood samples for pharmacokinetic analysis of ticagrelor and its metabolite AR-C214910XX will be obtained of each treatment period at the following time points:

- Pre-dose (within 5 minutes prior to dosing), 0.5, 1, 2, 3, 6, and 12 hours post dose.

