### **13. IMPORTANT MEDICAL PROCEDURES TO BE FOLLOWED BY THE INVESTIGATOR**

The principal investigator(s) is responsible for ensuring that procedures and expertise are available to handle medical emergencies during the study. **A medical emergency usually constitutes an SAE and should be reported as such.** In the case of a vascular event, the patients should be discontinued from the study if administration of a prohibited concomitant medication treatment with PCI or CABG or other major surgery is needed.

The AstraZeneca representative will work with the investigator to compile all the necessary information and ensure that the appropriate AstraZeneca Patient Safety Department receives a report by Day one for all fatal and life-threatening cases and by Day five for all other SAEs.

All Serious Adverse Events (SAE) must be reported to Clinical Patient Safety, AstraZeneca Marketing Company within one day (that is immediately but not later than the end of the next business day) by fax. Clinical Drug Safety will forward the SAE report to the applicable AstraZeneca R&D. The monitor should also be informed when an SAE has occurred.

Follow-up information on SAEs must also be reported by the investigator within the same time frames.

The investigator and/or Sponsor are responsible for informing the Ethics Committee and/or the Regulatory Authority of the SAE as per local requirements.

For Serious Adverse event reporting, complete the SAE report and fax the report to the appropriate Patient Safety department.

There is no known antidote to reverse the effects of ticagrelor. The average half-life of ticagrelor is approximately 12 hours, so blood levels of ticagrelor should be low by 48 to 72 hours (ie, 4 to 6 half-lives) after discontinuation. Platelet transfusions may be given. It is not known if new platelets may be inhibited by ticagrelor as long as it is circulating in blood.

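### With 12 h sampling gaps, the linear trapezoidal rule in section 11.2 overstates Day 1 AUC0-t and AUC of ticagrelor (parent) by about 1% to 4%

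*Protocol*

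**What the plan says.** Section 11.2 names one integration rule: "AUC will be calculated using the linear trapezoidal method up to the last measurable concentration", "and thereafter by extrapolation of the terminal elimination phase to infinity". It gives no logarithmic rule for the declining part of the curve. The terminal slope comes from "log-linear regression of the terminal portion of the concentration-time profile using at least 3 time points".

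Section 6.4.1 (also Tables 2 and 5) places the single-dose samples at pre-dose and at "0.5, 1, 2, 3, 6, 12, 24, 36, and 48 hours post dose". The gaps after 6 h are therefore 6, 12, 12 and 12 h. The Day 7 samples are "Pre-dose (within 5 minutes prior to dosing), 0.5, 1, 2, 3, 6, and 12 hours post dose", with one 6 h gap and no 12 h gap.

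Two half-lives are stated for ticagrelor. Section 1.1 says that the value "of the parent compound is approximately 7 hours"; section 13 says "The average half-life of ticagrelor is approximately 12 hours".

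Day 1 AUC0-t and AUC are secondary outcome variables in the synopsis. The accumulation ratio in section 11.2 uses AUC(0-12h) on both days. Section 12.3 states that the data are descriptive and that no test underlies the sample size.

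**The concern.** Once absorption is over, plasma concentration falls in a convex curve, and a straight line between two points on a convex curve lies above it. The excess grows with the gap measured in half-lives, and the Day 1 schedule has three gaps of 12 h. Both AUC0-t and AUC of the parent drug carry that excess.

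Determining the single-dose pharmacokinetics in this population is a secondary objective. In a descriptive study the estimate is itself the result, and a bias of this kind does not shrink with more patients.

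**Working it through.** The protocol states no AUC value or AUC error, so there is no figure of its own to reproduce.

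**Inputs from the protocol.** Day 1 times 0, 0.5, 1, 2, 3, 6, 12, 24, 36 and 48 h (section 6.4.1); half-life 7 h (section 1.1) or 12 h (section 13); linear trapezoid to the last measurable concentration, then extrapolation (section 11.2).

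**Assumptions, not in the protocol.** One-compartment profile with first-order absorption, ka 0.5 to 3 per h (tmax about 1.2 to 4.9 h), no assay noise, all samples to 48 h measurable, terminal slope from the last three points.

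**Step 1: error over one interval of pure exponential decline.** With k = ln 2 / half-life and gap d, linear / true = (kd/2) × (1 + e^(−kd)) / (1 − e^(−kd)).

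| Half-life | Gap | Gap in half-lives | kd | Linear / true |
|---|---|---|---|---|
| 7 h | 6 h | 0.86 | 0.594 | 1.029 |
| 7 h | 12 h | 1.71 | 1.188 | 1.115 |
| 12 h | 6 h | 0.50 | 0.347 | 1.010 |
| 12 h | 12 h | 1.00 | 0.693 | 1.040 |

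**Step 2: a whole Day 1 curve.** C(t) = ka/(ka − k) × (e^(−kt) − e^(−ka·t)), in units of dose over volume, with ka = 1.5 per h.

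- Half-life 7 h: linear AUC0-48 is 10.405 and the true value is 10.006, so +4.0%. Adding C48/λz = 0.093 gives 10.498 against a true AUC of 10.099, also +4.0%.
- Half-life 12 h: 16.482 against 16.187, so +1.8%. Adding 1.125 gives 17.607 against 17.312, so +1.7%.

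Most of the excess arises between 12 and 24 h: 2.6 of the 4.0 points at 7 h and 1.1 of the 1.8 points at 12 h.

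**Step 3: range over ka 0.5 to 3 per h.**

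| Quantity (ticagrelor, Day 1) | Linear rule, 7 h | Linear rule, 12 h | Linear-up/log-down, both half-lives |
|---|---|---|---|
| AUC0-48 | +3.5% to +4.0% | +1.3% to +1.8% | −0.4% to −1.4% |
| AUC | +3.4% to +4.0% | +1.2% to +1.7% | −0.3% to −1.4% |
| AUC(0-12h) | −1.1% to +0.5% | −1.5% to −0.2% | −0.7% to −2.1% |

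The last row matters for the fix. Over 0 to 12 h the linear rule is at least as close to the truth.

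**Step 4: sensitivity.**

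- If the last measurable sample is at 24 h, the parent error up to that sample is +0.5% to +3.2%.
- Three assumed biexponential profiles gave +3.4% to +5.0% with the linear rule and −0.2% to +0.6% with linear-up/log-down.
- The accumulation ratio shifts by +0.3% to +1.2% under the linear rule.
- For the metabolite, with an assumed half-life of 3 to 12.7 h and 0 to 100% formed at absorption, the linear AUC0-48 error runs from −2.3% to +7.5%. Its sign is not fixed.

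**The case against.** The linear rule is explicit, pre-specified and in common use. Pairing it with a log-linear terminal slope is ordinary non-compartmental practice, so section 11.2 does not contradict itself. The pharmacokinetic outcomes are secondary and descriptive, and a shift of 1% to 4% overturns no stated conclusion. The alternative rule carries a small negative bias of its own. All of this stands, and it is why the point is minor.

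Four stronger readings might be inferred, and the documents do not support them:

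- **That the metabolite AUC is inflated too.** The documents give no kinetics for AR-C124910XX. Where it is formed slowly from circulating parent, the linear rule can understate its AUC. In one assumed set (parent half-life 7 h; metabolite 3, 6 or 8.5 h; ka 1 to 2 per h) the linear error in AUC was −0.2% to +1.5%, against −1.3% to −3.2% for linear-up/log-down.
- **That every falling interval is over-counted.** Just after the peak the curve is still concave. With ka 0.8 per h and a 7 h half-life, the 3 to 6 h interval is under-counted by 1.7%.
- **That the comparison of Day 7 with Day 1 is distorted.** Section 3.2 says the design "allows Day 7 results to be compared with the Day 1 dose of each drug dose level", but no ratio of Day 7 AUC(0-12h) to Day 1 AUC is defined. The accumulation ratio that is defined uses AUC(0-12h) on both days.
- **That dose comparisons are biased.** Rule and schedule are the same in all three groups, so at equal half-life the error is a common factor.

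What the objection does not remove is a one-directional error in two named secondary outcomes for the parent drug, which a change of integration rule largely avoids.

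**Conclusion.** The point holds for ticagrelor only, as a minor improvement. The linear rule at the protocol's times overstates Day 1 AUC0-t and AUC of the parent by about 4% if the half-life is 7 h and by 1% to 2% if it is 12 h. It overstated both in every parent scenario examined.

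The size rests on an assumed one-compartment oral profile and on which of the two stated half-lives applies; sections 1.1 and 13 should be reconciled. No effect of consequence is shown for the accumulation ratio or for comparisons between dose groups, and neither the sign nor the size is established for the metabolite.

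**What to change.** In section 11.2:

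- Calculate Day 1 AUC0-t and AUC of ticagrelor by the linear trapezoidal rule while concentrations rise and the logarithmic rule while they fall (linear-up/log-down).
- Use the same rule for both analytes when reporting the metabolite AUC and the metabolite:parent AUC ratio, so that the ratio does not mix methods. This is for consistency; greater accuracy for the metabolite is not claimed.
- List the linear-rule values of both analytes alongside, for comparison with other studies.
- Keep the linear rule for AUC(0-12h) on both days, and hence for the accumulation ratio, and for the IPA AUEC in section 11.3.

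The cost is a few lines of text and a setting in the non-compartmental software, with no extra samples or patients. The downside is that parent AUCs come out slightly lower and differ in method from any earlier linear-rule results; the supplementary listing covers that.
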